The results of this research study may be presented at scientific or medical meetings or published in scientific journals. However, your identity will not be disclosed.

Patient information may be provided to Federal and other regulatory agencies as required.

Alternative Treatments and Procedures

There are other treatments available for your depression. These include a variety of antidepressant medications such as fluoxetine (Prozac), paroxetine (Paxil), bupropion (Wellbutrin), and psychotherapies (talk therapies), such as cognitive-behavioral therapy (CBT). These treatment options also include Electroconvulsive therapy (ECT) and Transcranial Magnetic Stimulation (TMS).

2.3.2. Known Potential Benefits:

Possible gains for the subject are reduction in suicidal ideation and behavior with active treatment. All patients will receive one or more agents that have been shown to have anti-suicidal effects. Since there are two potential innovative treatments for suicidal behavior, considerable information will be generated as to the anti-suicide effects of opioid agents.

3. Objectives and Endpoints:

OBJECTIVES	MEASURE DESCRIPTION	TIMEFRAME
Primary		
Change in Scale for Suicide Ideation total scores will be analyzed as the primary outcome measure using analysis of variance model for repeated measures.	The model will include the difference in total scores on the suicidality measure from days 3 to 31 as a within subject effect, treatment, and time, as well as time x treatment interaction. The model will include Day 3 score as well. The total scores range from 0 to 38, with higher values indicating a greater risk of suicide. All effects will use $p < .05$ for simple effects and $p = 0.1$ for interactions, using a sample size of 60, the hypothesis test will be fully powered (i.e., 80%) to detect effect sizes of 0.35 or greater.	Change from Day 3-31 and add to the model the Day 0 to 3 change in response to ketamine.
Secondary		
The secondary outcome will be change in depression measures (MADRS and HAMD) from day 1 to day 31.	The model will include the difference in total scores on the depression measures from days 3 to 31 as a within subject effect, treatment, and time, as well as time x treatment interaction. The model will include Day 3 score as well.	Change from Day 3-31 and add to the model the Day 0 to 3 change in response to ketamine.
Other		

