Analysis of baseline characteristics: Demographic data including age, gender, ethnicity, diagnosis, treatment history, and previous suicide attempts will be summarized using descriptive statistics (means, standard deviation, range for continuous variables and frequency counts for categorical variables). Mean baseline scores on primary and secondary symptom measures (e.g., SSI, MADRS) as well as other related measures will be presented in a table. These demographics will be provided for the ITT all patients randomized and for the mITT efficacy evaluation sample.

Analysis of primary endpoint: The primary endpoint of this RCT, submitted a priori in clinical trials.gov, is reduction in SSI suicidality score from baseline to day 31. All randomized participants received a standard ketamine infusion, and SSI will be assessed at day 1 prior to the infusion and at day 3. Subsequently, patients will receive 4 weeks of either daily low-dose buprenorphine or placebo with doses increased weekly accompanied by weekly clinical assessments. H0, the null hypothesis, is that mean SSI suicidality ratings will not differ between patients randomized to low-dose buprenorphine and patients randomized to placebo. The research hypothesis H1 is patients randomized to the buprenorphine condition will have significantly lower SSI scores by the end of treatment (day 31). Null hypothesis testing and p-values were planned only for the primary and secondary hypotheses with consideration of type 1 error risk. For all analyses, effect sizes will be emphasized using Glass's estimate, a variant of Cohen's d that corrects for the unequal variances often observed in intervention studies or Number Needed to Treat.

Statistical analysis of the primary outcome will be based on the modified intention to treatment (mITT) population, defined as participants who received at least one SSI assessment during the active

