treatment phase. Although ITT estimates theoretically have less bias, the mITT is a conservative decision for the current design in which all patients will first receive ketamine. Including patients who only received ketamine and completed no assessments past the ketamine phase (days 1 to 3) would provide no information regarding response to follow-on buprenorphine or placebo. Moreover, given the known antidepressant effect of ketamine on suicide, their inclusion would likely underestimate the projected means at time points during the post-ketamine evaluation of 4 weeks of follow-on buprenorphine vs placebo.

Repeated measurements of the SSI will be compared across treatment groups using a linear mixed-effects model. The mixed model makes use of all available SSI scores across the study timepoints to estimate group differences in means. The model will include fixed effects of treatment group, time, time by treatment group interaction, and a random effect of participant intercept. An unstructured covariance matrix, or a first order auto-regressive structure, will be used based on relative model fit according to the information criterion index. This model parameterization is suited for testing of between-group differences over repeated measurements, consistent with the primary study hypothesis. The SPSS syntax is:

MIXED SSI with time treatment

/Criteria=CIN(95) MXITER(100) MXSTEP(10) SCORING(1)

SINGULAR (0.0000000001) HCONVERGE(0, ABSOLUTE) LCONVERGE(0, ABSOLUTE),
PCONVERGE(0.00000001, ABSOLUTE)

/FIXED time time*treatment | SSTYPE(3)

/METHOD=ML

/RANDOM=INTERCEPT time | PARTICIPANT COVTYPE(UN).

The result of the hypothesis test for efficacy of Ketamine followed by Buprenorphine will be determined by the statistical significance of the treatment by time interaction (two-sided $\alpha=.05$). Only if group differences are deemed statistically significant on the prespecified primary outcome, a supplemental analysis of clinical significance will be conducted by calculating the proportion of responders, defined as a 50% or greater reduction in SSI suicidality ratings from baseline to day 31, in each of the two treatment groups. These proportions will be compared with a 2x2 chi-squared test.

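### Sections 3 and 9 specify different primary SSI analyses (model, covariates, window and interaction threshold), and nothing says which governs

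*Combined protocol and SAP*

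**What the plan says.** Both texts are current, and both concern the primary SSI outcome.

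**Section 3 (Objectives and Endpoints), primary row.** "Change in Scale for Suicide Ideation total scores will be analyzed as the primary outcome measure using analysis of variance model for repeated measures". The outcome is the Day 3 to Day 31 difference, with treatment, time and their interaction as terms. On covariates: "The model will include Day 3 score as well", and the timeframe column reads "Change from Day 3-31 and add to the model the Day 0 to 3 change in response to ketamine". On thresholds: "All effects will use $p < .05$ for simple effects and $p = 0.1$ for interactions".

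**Section 9 (Statistical Considerations), Analysis of primary endpoint.** "Repeated measurements of the SSI will be compared across treatment groups using a linear mixed-effects model". On the data that enter it, the section adds: "The mixed model makes use of all available SSI scores across the study timepoints to estimate group differences in means". On terms: "The model will include fixed effects of treatment group, time, time by treatment group interaction, and a random effect of participant intercept". The population is modified intention to treat, "defined as participants who received at least one SSI assessment during the active" phase of treatment. The endpoint is the reduction from baseline to Day 31, and efficacy is decided by the treatment by time interaction at two-sided 0.05. Neither Section 3 covariate appears in the prose or in the SPSS syntax.

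Neither section refers to the other. Section 9 assumes data missing at random for its mixed models. Section 3 is silent on missed visits.

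**The concern.** A trial with one primary test needs one specification of it. Here an analyst could follow either section and claim to be following the protocol, yet fit a different model to a different outcome window, with different adjustment and a different significance threshold. Section 9 confines p-values to the pre-specified outcomes in order to limit type 1 error. That protection weakens if the primary test itself can be chosen after the data are seen.

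The interaction threshold matters most, because Section 9 makes the interaction the deciding test. The choice of model could also change who is analysed, if the Section 3 method were run on complete cases only.

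**Working it through.** **1. The plan's own figure.** The plan gives no missed-visit rate, so there is none to reproduce. Both sections quote 80% power for an effect size of 0.35 with 60 patients. A simple two-group check (30 per arm, normal approximation, power = Φ(d√(30/2) − z)) gives:
- 0.35 as d, two-sided 0.05: Φ(1.356 − 1.960) = 27%
- 0.35 as d, alpha 0.10: Φ(1.356 − 1.645) = 39%
- 0.35 as f, so d = 0.70, two-sided 0.05: Φ(2.711 − 1.960) = 77%

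None of these returns 80%. Repeated-measures calculations reach it only with correlations and visit counts that the plan does not state. The power statement therefore cannot show which of the two analyses was intended, and it does not decide this point.

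**2. The two specifications side by side.**

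| Item | Section 3, primary row | Section 9 |
|---|---|---|
| Model | Repeated-measures ANOVA | Linear mixed-effects model |
| Outcome | SSI change, Day 3 to 31 | SSI scores; endpoint baseline to Day 31 |
| Covariates | Day 3 score; Day 0 to 3 change | Neither listed |
| Interaction threshold | 0.1 | 0.05, two-sided |
| Population | Not stated | mITT |
| Missing data | Not stated | Missing at random |

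Section 1.3 adds a third wording of the window, Day 1 to Day 31. The Day 0 used in Section 3 is not a column in the Section 1.5 schedule.

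**3. Threshold.** Under the null hypothesis a valid p-value is uniform, so P(0.05 < p < 0.10) = 0.10 − 0.05 = 0.05. If the interaction decides, as Section 9 says, about one null trial in 20 would pass at Section 3's threshold and fail at Section 9's. The false-positive rate is 0.10/0.05 = 2 times as high under Section 3.

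**4. Window, with no visit missed.** For raw scores, (Day 31 − Day 1) = (Day 31 − Day 3) + (Day 3 − Day 1). Randomization is at Day 3, so the arms' difference in the last term is zero on average but not in any one sample. With 30 per arm its standard error is s√(1/30 + 1/30) = 0.258s, where s is the SD of the Day 1 to 3 change. The plan does not give s. Assuming s = 4.5 to 9.0 (the upper value borrows the SSI SD quoted from the cited buprenorphine trial in Section 9), the standard error is 1.2 to 2.3 points. This describes unadjusted change, not either full model. It shows that the window alone can move the estimate.

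**5. Analysed set, only if the ANOVA is run on complete cases.** The on-treatment visits are Days 10, 17, 24 and 31 (Section 1.5). With an assumed miss rate q per visit, independent across visits, the number with any miss is 60 × (1 − (1 − q)^4). The bounds are 60q if the same people miss all four visits, and 60 × 4q if no one misses twice.

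| q (assumed) | Independent | Same people | No overlap |
|---|---|---|---|
| 3% | 6.9 | 1.8 | 7.2 |
| 5% | 11.1 | 3 | 12 |
| 10% | 20.6 | 6 | 24 |

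In the same-people case those participants have no SSI after Day 3 within the treatment phase. Section 9's mITT would exclude them too, and the two analysed sets would coincide.

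**The case against.** Section 9 is the dedicated statistical section. It gives the population, model, syntax, deciding test and alpha, and it says its endpoint is the one registered in advance. Section 3 is an objectives table. Its ANOVA label may be a loose name for a mixed model, since it lists the same treatment, time and interaction terms. On that reading Section 9 governs and the label is a slip.

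Much of this stands. A reader might infer that the Section 3 ANOVA drops everyone with a missed visit, so that the plan contains a completer analysis alongside an mITT analysis. The documents do not say so. Deletion of incomplete cases is how a classical repeated-measures ANOVA usually behaves. But Section 3 says nothing about missed visits, the only primary population defined is the mITT, and Section 9's missing-at-random statement covers both primary and secondary endpoints.

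Independent misses are also a strong assumption. Visits have windows of 2 days either side, staff are to try to reschedule a missed visit within 24 hours, and a participant who misses one visit and cannot be reached counts as lost to follow-up (Sections 1.5 and 7.3). All of this points to fewer or clustered misses.

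A reader might also turn the smaller sample into a loss of power with a two-sample t-test. That figure would describe neither planned model, and the mixed model does not recover scores that were never collected.

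The objection does not remove the differences in covariates, window and interaction threshold. These remain whatever the Section 3 model is called.

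**Conclusion.** The point holds as a conflict between two specifications of the primary test. The p-value depends on the section followed, even with complete data. Where the interaction p lies between 0.05 and 0.10, so does the conclusion. That last statement takes the interaction as the deciding effect, which Section 9 says and Section 3 does not.

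A difference in the patients analysed is conditional. It requires both a complete-case ANOVA and missed visits. At illustrative independent miss rates of 3% to 10% per visit it would affect about 7 to 21 of 60, shrinking towards none as misses concentrate in people who miss every visit. The plan gives no miss rate, so this is a scale, not a forecast.

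The conflict should be corrected, mainly because it leaves the primary test open to choice and is cheap to remove.

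**What to change.** In the Section 3 primary row, replace the repeated-measures ANOVA with the Section 9 linear mixed-effects model on all available SSI scores in the mITT population. State that no complete-case analysis supports the primary conclusion.

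In the same edit:
- Delete the 0.1 threshold for interactions and cite Section 9's two-sided 0.05.
- Choose one outcome window and one covariate set, and state them identically in Sections 3 and 9 (and the window in Section 1.3). If the Day 3 score or the early change is kept, add it to Section 9's model and syntax, and tie Day 0 to a scheduled visit.
- Align the secondary row's model description, window and covariates with Section 9. That row does not name an ANOVA, but it gives Day 1 to 31 in one column and Day 3 to 31 in the others.

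Changing the model name alone would leave the other conflicts standing. Section 9 also needs to be a single target: its prose has a treatment main effect and a random intercept, while its syntax omits that main effect and adds a random slope for time.

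The cost is wording in the Section 3 table and a few lines elsewhere, with no new data. The choices should be fixed before treatment codes are opened.

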We will closely monitor AE's on a continuous basis, and involve the DSMB in assessing whether any AE is unexpected, or more severe than expected (at a rate greater than what would be expected by chance). Should we identify any AE that meets one of those two criteria or should we have any unexpected SAE's we will notify currently enrolled participants, and change our consent to include the pertinent information.

8.3.8. Reporting Pregnancy:

We will not include pregnant women in this study. If the participant is of childbearing potential and not already pregnant, the participant must agree to use adequate contraception (hormonal / barrier method

of birth control or abstinence) prior to study and for the duration of the study participation. During the screening phase of this study, participants of childbearing potential will be administered a pregnancy test; a negative pregnancy test will be required to confirm eligibility for study participation and will be done prior to receiving ketamine. If a participant becomes pregnant or suspects she is pregnant while participating in the buprenorphine/placebo phase of the study, she should inform the research staff immediately via in-person meeting, telephone call, or email. If a participant reports pregnancy occurring during the study period in which the participant was exposed to buprenorphine/placebo, research staff will stop the study visit and then notify the principal investigator.

9. Statistical Considerations:

Null hypothesis statistical testing (NHST) and p-values were planned only for the pre-specified primary (SSI suicidality scores) and secondary efficacy measure (MADRS and HDRS depression scores) to minimize type 1 error risk. For any supplemental analyses (e.g, clinical endpoints), NHST is only employed if the prespecified efficacy analyses are statistically significant. For all research questions, effect sizes rather than p-values are emphasized. Effect size for the prespecified efficacy endpoints will use Glass's delta estimate, a variant of Cohen's d that corrects for the unequal variances often observed in intervention studies. Effect size for clinical analyses with a dichotomous outcome will be expressed as Number Needed to Treat (NNT).

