Analysis of secondary endpoints: The secondary outcome will compare treatment groups on the change in depression symptoms from baseline to day 31 using weekly scores from the MADRS and HDRS. A similar mixed-effects model used for the primary endpoint will be applied. The trajectories of MADRS and HDRS mean scores will be compared between the two groups in the mixed model with statistical significance determined by the p-value for the treatment group by time interaction term. If the groups differ significantly on the MADRS scores, the proportion of responders (i.e., >50% or greater reduction from

baseline to day 31) will be statistically with a 2x2 chi-squared test. The MADRS depression assessment includes one item that assesses suicidal thoughts. Mean scores and standard deviations on this item will be calculated for the K+Buprenorphine and K+Placebo groups, and effect sizes will be calculated using Glass's formula.

Analysis of safety endpoints: Frequencies of side effects, adverse events, and serious adverse events observed during the active treatment phase will be summarized by group, and the most commonly reported adverse events will be tabulated. Changes in suicidality and withdrawal symptoms during the 2-week post intervention phase (days 38 and 45) will be described with means, standard deviations, and ranges for the SSI and MADRS, as well as for clinician and patient ratings of withdrawal (COWS and SOWS). These measures will be compared across groups using independent measures t- tests. No type 1 error correction is planned for safety analyses.

Evaluation of treatment blind: Two-weeks post-intervention (day 45), patients will be asked to endorse one of the following: I think I was taking active medication; I think I was taking placebo; I am unsure if I was taking an active medication or a placebo. Frequency counts and percentages will describe the correct and incorrect guesses.

Missing data: For both primary and secondary endpoints, the mixed-effects models implicitly assume data missing at random. Sensitivity analyses will only be conducted if necessary (e.g., if the missingness is non-ignorable due to high frequency of missingness or if data are not missing at random).

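### The significance level for the primary treatment-by-time interaction is stated as 0.1 in Section 3 and as two-sided 0.05 in Section 9, and no text says which governs

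*Combined protocol and SAP*

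**What the plan says.** Section 3 (Objectives and Endpoints, primary row) analyses change in SSI from Day 3 to Day 31 with a repeated-measures analysis of variance. Its terms include "treatment, and time, as well as time x treatment interaction"; no other interaction is listed. The same row sets the levels: "All effects will use $p < .05$ for simple effects and $p = 0.1$ for interactions". It continues directly to the claim of 80% power for effect sizes of 0.35 or more with 60 participants. It does not say whether the levels are one- or two-sided.

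Section 9 (Analysis of primary endpoint) uses a linear mixed model: "The model will include fixed effects of treatment group, time, time by treatment group interaction, and a random effect of participant intercept". The efficacy result "will be determined by the statistical significance of the treatment by time interaction", at a two-sided alpha of 0.05.

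Two gates depend on that result. The opening paragraph of Section 9 says that for supplemental analyses "NHST is only employed if the prespecified efficacy analyses are statistically significant". For the SSI responder comparison it says: "Only if group differences are deemed statistically significant on the prespecified primary outcome, a supplemental analysis of clinical significance will be conducted".

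For MADRS and HDRS, Section 9 (Analysis of secondary endpoints) applies a similar mixed model, with "statistical significance determined by the p-value for the treatment group by time interaction term". No level is given there.

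**The concern.** The test that decides the trial should have one threshold, fixed before the data are seen. Here the same interaction on the same outcome has two, a factor of two apart. If the observed p-value were 0.07, a reader of Section 3 would call the interaction significant and a reader of Section 9 would not. The plan gives no basis for settling the disagreement, so it would be settled with the result in view. The consequences go beyond the headline: whether the SSI responder chi-squared test and other supplemental tests may be run at all turns on the same call.

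**Working it through.** **1. The plan's own figure.** Sections 3 and 9 (Sample size justification) both state 80% power for an effect size of 0.35 with N = 60. If that figure pointed to one alpha, it would show which level the design used.

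Inputs: 30 per arm (study population paragraph of the synopsis); effect size 0.35, metric not stated; alpha not stated in Section 9. I take a simple two-group comparison with 58 degrees of freedom. The noncentrality is d × √(30 × 30 / 60) = d × √15, and power = P(|T| > t at 1 − α/2). I read 0.35 as Cohen's d, then as Cohen's f (d = 2f = 0.70). The sample size for 80% power uses n per arm = 2(z at 1 − α/2 + 0.842)² / d².

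| Reading of 0.35 | Noncentrality | Power, two-sided 0.05 | Power, two-sided 0.10 | n per arm for 80%, at 0.05 / 0.10 |
|---|---|---|---|---|
| d = 0.35 | 1.356 | 26.6% | 38.2% | 129 / 101 |
| f = 0.35, d = 0.70 | 2.711 | 76.0% | 85.0% | 33 / 26 |

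None of the four is 80%. Repeated-measures assumptions can come close, but they point both ways. A between-group test with f = 0.35, two time points and correlation 0.7 gives 82% at alpha 0.05. A change score with d = 0.35 and correlation 0.85 gives 79.7% at alpha 0.10. Those correlations and time points are my assumptions; the documents give none. The power claim therefore does not identify the alpha.

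**2. Can sidedness reconcile the levels?** Section 9 is explicitly two-sided 0.05. If Section 3's 0.1 is two-sided, it equals one-sided 0.05. If it is one-sided, it equals two-sided 0.20. Neither gives two-sided 0.05.

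**3. Could the 0.1 belong to another interaction?** A lenient level is sometimes kept for moderator interactions. Neither the Section 3 primary row nor the Section 9 primary model lists one. Time by treatment is the only candidate.

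**4. Size of the disputed range.** With a two-sided test it is 0.05 ≤ p < 0.10, that is |z| from 1.645 to 1.960, or |t| from 1.672 to 2.002 on 58 degrees of freedom. The chance of landing there is power at 0.10 minus power at 0.05:

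- no effect: 10.0% − 5.0% = 5.0%
- d = 0.35: 38.2% − 26.6% = 11.6%
- d = 0.70: 85.0% − 76.0% = 9.0%

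The value 0.70 is also the cited buprenorphine trial's planning effect (6.3 / 9.0). Both effect sizes are illustrations, and a two-group t test only approximates the mixed-model interaction test.

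**The case against.** The best defence is that Section 9 is the more specific text and has the only rule that ties a p-value to a conclusion about efficacy. Section 3 lists levels for model effects and never says the interaction decides the trial. The two sections also fit different models, so their p-values would not be identical. Section 9 says it restricts testing to limit type 1 error, its code requests 95% intervals, and its responder gate follows directly after the two-sided 0.05 rule. Read alone, Section 9 is clear.

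Much of this stands. It shows that 0.05 is the likelier intention, and it rules out some stronger readings:

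- A reader might infer that the plan declares p = 0.07 both a success and a failure. Section 3 supports only that such a result is significant at its stated level; success there is an inference.
- A reader might infer that 0.1 also governs MADRS and HDRS, and that three interaction tests at that level carry a family-wise error of 1 − 0.90³ = 27%. The documents do not support this. The sentence with 0.1 is in the primary row, the secondary row repeats the model wording without it, and Section 9's reference to a similar model points at least as naturally to 0.05. The 27% also assumes independence among three scales, two of which measure depression.
- A reader might infer that the 80% power was computed at 0.10. The working shows that it cannot be told.

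What the defence does not supply is a statement that Section 9 overrides Section 3. The difference in models adds to the ambiguity and does not remove it.

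**Conclusion.** The concern holds in a limited form: one interaction, one primary outcome, two stated levels, and no order of precedence. That part follows from the text alone and needs no assumption. Under the null, the nominal error rate is 10% or 5% depending on the section followed. The 9% to 12% chance of a disputed p-value under an effect rests on the assumed d of 0.70 or 0.35, 30 analysed per arm and a simple two-group contrast. MADRS and HDRS lack a stated level, which is a gap and not a second contradiction. Because the conflict concerns the threshold of the only primary test, it should be corrected before unblinding, even though Section 9 makes the probable intention clear.

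**What to change.** In Section 3, delete the 0.1 level for interactions. In both Section 3 and Section 9, state that the primary treatment-by-time interaction is tested at two-sided 0.05; this keeps Section 9's explicit rule and fits its aim of limiting type 1 error.

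Wherever the 80% power claim appears (Section 3 primary row and Section 9, Sample size justification), state the alpha it used. If it was computed at 0.10, restate the power at 0.05.

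State the same two-sided 0.05 for the MADRS and HDRS interactions. A fixed testing order for those two scales is a separate, optional choice and is not needed to resolve this conflict.

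The cost is a few sentences and, if the calculation used 0.10, a lower stated power (about 9 to 12 percentage points in the two illustrations above). Nothing is lost relative to the rule Section 9 already sets.
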